2.5 Informed Consent Process and Enrollment

Subjects will be asked to review the post treatment instructions prior to signing the informed consent form and their involvement in the study. They must also review the site's COVID-19 procedures and agree to follow protocols put in place at the site relating to COVID-19. Subjects who sign the informed consent will be screened to confirm eligibility and, if eligible, will be assigned a subject identification number. Subjects will be de-identified through their subject identification number, which will be stored in a secure location. Subject identification numbers will be generated chronologically and assigned only to subjects who have met all the study selection criteria and have signed the informed consent form. The informed consent will be obtained prior to a subject's involvement in any study related procedures. A subject will be considered enrolled in the study once they have signed the informed consent form.

The following post treatment instructions will be reviewed with subject:

- You can return to a normal lifestyle immediately after treatment including light athletic workouts but avoid extreme exercise or activities that may reinjure the damaged area through overuse. The inflammation may have eliminated pain but it takes time to heal.
- You can continue previously prescribed therapies, such as stretching.
- Avoid ice and anti-inflammatory medicine (i.e. NSAIDs, such as Ibuprofen) for several days after therapy as this may reduce outcomes.
- Drink lots of water.
- You may feel tired after a SoftWave treatment.
- You may experience a tingling sensation in the treatment area for several days after therapy. This is good.
- You may experience mild soreness or stiffness during the next 48 hours. This is normal.

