2.8 Post Treatment Procedures

- Adverse events will be documented after treatment.
- Photographs may be taken post treatment.
- Post treatment instructions will be reviewed with the subject.

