2.14 Adverse Event Recording

All data captured must be supported by the Investigator's timely assessment and documentation of the adverse event in the case report forms or source documents. All documented adverse events will be reviewed by the Sponsor or designee to determine whether the adverse event meets regulatory reporting requirements and to ensure timely adverse event reporting to meet local and global regulatory requirements. All adverse events must be followed until their resolution.

Adverse Events Pertaining to the SoftWave Device:

Potential adverse effects associated with shock wave treatments include those listed below:

- Transient moderate increase in pain
- Redness and swelling
- Hematoma and petechial hemorrhage
- Headaches and fainting during extracorporeal shock wave treatments
- Short-term hypoesthesia
- Nausea during therapy
- Tingling during therapy

Adverse Events Pertaining to the Marker:

Using a marker has minimal risks and may produce effects on the body such as redness or a rash.

Adverse Events Pertaining to Ultrasound Gel:

The gel is a water-based gel that may be placed on the skin during treatment. No known adverse events are documented. However, an allergic reaction is always possible when placing a topical gel onto the skin. Allergic reaction may include a mild reaction such as skin redness, irritation, or hives.

Biopsies

Complication with biopsies can include pain, redness, swelling, infection, bleeding, scarring and skin texture irregularities.

Lidocaine

You may experience pain and numbness at the site of the injection. You may also experience redness, rash, infection, skin damage or nerve damage at the site of the injection. You may experience temporary loss of sensation and muscle function at the site of injection.

1% lidocaine (Lidocaine) with Epinephrine Injection

Lidocaine with epinephrine contains the preservative sodium metabisulfite which may cause allergic-type reactions including anaphylactic symptoms such as itching, hives, swollen areas of the body, and/or trouble breathing and life-threatening or less severe asthmatic episodes in certain susceptible people.

Other Cautions:

Incomplete response or no response may occur since some subjects may not respond to treatment.

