2.15 Statistical Analysis**2.15.1 Hypothesis**

For this study to be considered a success, the average pain score is acceptable to the Physician as it relates to the type of treatment.

For additional objectives to be considered a success, the following criteria must be met:

- The side effect profile (adverse events) is acceptable to the Physician as it relates to the type of treatment.
- The subject satisfaction rates at the follow up visit will be $\geq 80\%$ (optional).
- Correct identification of pre-treatment images when compared to post treatment (30 and/or 90 day) images will be $\geq 80\%$ (optional).
- Successful collection of biopsies (optional).
- Successful collection of treatment assessment questionnaires (optional).

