14.0 ADVERSE REACTIONS DEFINITIONS AND REPORTING REQUIREMENTS

All adverse events that occur, starting from the time of the first treatment, will be recorded in the source documents and Case Report Forms (CRF).

Adverse Events (AE) occurring will be captured and followed until the condition resolves, stabilizes, is otherwise explained, or the subject is lost to follow-up. Subjects will be instructed that they may contact the Investigator at any time throughout the course of the study.

The Investigator and/or designated study staff will review each event and assess its relationship to the study device (not related, unlikely, possible, probable, and highly probable). The following definitions will be used for rating relationship to the SoftWave treatments:

- Not related – The event is clearly related to other factors such as the subject's clinical state, therapeutic interventions, or concomitant medications administered to the subject.
- Unlikely – The event was most likely produced by other factors such as the subject's clinical state, therapeutic interventions, or a concomitant medication administered to the subject; and does not follow a known response pattern to the investigational product.
- Possible – The event follows a reasonable temporal sequence from the time of investigational product administration; **and/or** follows a known response pattern to the study sampling sessions; **but** could have been produced by other factors such as the subject's clinical state, therapeutic interventions, or concomitant medications administered to the subject.
- Probable – The event follows a reasonable temporal sequence from the time of investigational product administration; **and** follows a known response pattern to the investigational product; **and** cannot be reasonably explained by other factors such as the subject's clinical state, therapeutic interventions, or concomitant medications administered to the subject.

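### The post-treatment instructions call tingling for several days good and soreness normal without asking subjects to report either, so mild adverse events may go unrecorded

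*Combined protocol and SAP*

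**What the plan says.** **Instructions to subjects.** Section 2.5 (Informed Consent Process and Enrollment) says of tingling: "You may experience a tingling sensation in the treatment area for several days after therapy. This is good". Of soreness it says: "You may experience mild soreness or stiffness during the next 48 hours. This is normal". It also warns of tiredness. No item in the list asks the subject to report any of these effects.

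**When subjects see them.** Before consent, under 2.5: "Subjects will be asked to review the post treatment instructions prior to signing the informed consent form". They are gone over again at screening (2.4) and after treatment (2.8): "Post treatment instructions will be reviewed with the subject".

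**Listed device effects.** Section 2.14 (Adverse Event Recording) includes "Tingling during therapy" and "Transient moderate increase in pain". Tiredness, stiffness and tingling after therapy are not on the list.

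**Recording rule.** Section 14.0 states: "All adverse events that occur, starting from the time of the first treatment, will be recorded in the source documents". Its lowest severity grade, mild, covers easily tolerated events. Sections 2.8 and 2.9 call for adverse events to be documented after treatment and at follow-up. The schedule in 2.13 marks an adverse event assessment at every visit.

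**Use of the data.** Section 2.15.1 makes this a success criterion among the additional objectives: "The side effect profile (adverse events) is acceptable to the Physician as it relates to the type of treatment". It is the only criterion in that list not marked optional. Section 2.15.6 summarises safety as number and percent of patients, without statistical comparison.

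**The concern.** A subject who has been told that a sensation is good has little reason to mention it. That would matter little if staff asked about each effect by name, or if the effects occurred while the subject was in the clinic. The protocol provides for neither. It gives no general definition of an adverse event, no symptom checklist, no standard question, and no rule on whether an effect foretold in the instructions counts as an adverse event.

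At stake is the completeness of the mild-event counts. They feed the side-effect profile that the Physician judges under 2.15.1, in a study meant to support additional marketing claims (1.1).

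There is a second, smaller consequence. Causality grading in 14.0 relies on whether an event follows a known response pattern, and a separate reporting route depends on whether a complication was unforeseen. Because 2.5 and 2.14 name different effects, the same event could be classified differently depending on which section is consulted.

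**Working it through.** No figure in the protocol bears on this point and can be reproduced. The sample size of 50 (2.15.2) is given without an event rate, and no acceptability threshold is stated. The check is therefore mainly a comparison of sections.

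**1. Do the two descriptions of expected effects agree?**

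| Effect | 2.5 instructions | 2.14 list |
|---|---|---|
| Tingling | for several days after therapy; called good | during therapy only |
| Soreness or stiffness | mild, next 48 hours; called normal | not listed; nearest entry is a transient moderate increase in pain |
| Tiredness | may occur | not listed |

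They overlap in kind but differ in timing and degree.

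**2. When do the effects occur relative to the assessments?**
- An assessment made at the treatment visit comes before the 48 hours of soreness and the days of tingling have run.
- Treatments are 3 to 14 days apart (2.7). Soreness lasting 2 days would have ended 3 − 2 = 1 day to 14 − 2 = 12 days before the next treatment visit.
- After the last treatment, the next visit outside the biopsy portion is at 30 days (2.9), about 30 − 2 = 28 days after such soreness ended. The schedule in 2.13 marks that visit optional.
- Subjects may receive up to 5 treatments, so a subject could have only one. For that subject, outside the biopsy portion, every later scheduled assessment is marked optional.

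Capture therefore depends largely on recall and on the subject volunteering the symptom.

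**3. Illustration of direction only.** Expected recorded count = 50 × true rate × probability of reporting. The rates and reporting probabilities below are assumptions; none is in the documents.

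| Assumed true rate | All report | 75% report | 50% report | 25% report |
|---|---|---|---|---|
| 10% | 5.0 | 3.8 | 2.5 | 1.2 |
| 30% | 15.0 | 11.2 | 7.5 | 3.8 |
| 50% | 25.0 | 18.8 | 12.5 | 6.2 |

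For example, 50 × 0.30 × 0.50 = 7.5 recorded against 15 that occurred. Any shortfall lowers the recorded rate. How large it is in this study cannot be said.

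**The case against.** The strongest reply is that the protocol already requires what is being asked for. Section 14.0 demands that all adverse events be recorded, exempts none because they are expected, and grades mild ones. Assessments are scheduled at every visit, subjects are to be told they may contact the Investigator at any time, and nobody is told to withhold or omit anything. This stands, and it limits the point to a risk. It does not remove the risk, because a duty to record does not bring a symptom to the recorder's attention.

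A reader might infer that the instructions relabel listed side effects as good. The documents do not support that: 2.14 lists tingling during therapy, not for days after, and a moderate rise in pain, not mild soreness. The defect is a mismatch between the two sections.

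Telling subjects what to expect is proper, and the protocol does so elsewhere. The biopsy instructions in 2.10 also call slight redness and initial tenderness normal. They do, however, follow this with a request to contact the site if symptoms go further. The instructions in 2.5 have no such request.

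Three further limits are fair. Some listed effects, such as swelling or hematoma, can be seen by staff without being volunteered. Biopsy subjects may be seen as early as 1 or 3 days after the last treatment. The consent form and the Post Treatment Instructions are attachments that were not available here, so what subjects are told in total about reporting cannot be judged.

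**Conclusion.** The point holds as a credible risk of under-reporting of mild, short-lived effects, together with a mismatch between 2.5 and 2.14 that needs reconciling. It rests on three things: subjects receive the wording of 2.5 as printed, these effects mostly occur between visits, and no standard question asks about them. Any bias would make the side-effect profile look better than it is.

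Three stronger conclusions are not supported:
- **That adverse events are under-reported.** The documents contain no evidence of it, and 14.0 requires full recording.
- **That the side-effect criterion leans towards success.** The criterion has no threshold and rests on the Physician's judgement, so no change in a mild-event rate can be tied to a changed conclusion. The missing threshold is a separate and larger weakness.
- **That the primary pain result is affected.** The 0 to 10 score is asked directly as part of the treatment procedure (2.7) and does not depend on volunteered reports. An effect on satisfaction scores is likewise not shown.

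The size of the effect cannot be calculated. The counts tabulated above illustrate direction and should not be cited as estimates. The change is worth making because it is cheap and improves the data behind the one additional success criterion not marked optional.

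**What to change.** 1. In 2.5 and the Post Treatment Instructions attachment, delete the sentence that calls tingling good. Keep the information that these effects may occur, and leave the activity advice unchanged.
2. After the expected effects, add a neutral prompt, such as: *Please tell the study staff if you notice tiredness, tingling, soreness or stiffness, and how long it lasted.* With this prompt in place, the statement that soreness is normal can remain.
3. Reconcile the effects named in 2.5 with the list in 2.14, so that timing and degree agree and tiredness, stiffness and tingling after therapy are covered in both.
4. At each adverse event assessment already scheduled in 2.13, ask about these effects directly. Record them as adverse events with onset and duration, and state in 14.0 that this applies whether or not they were expected.

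The cost is a wording change, IRB approval of the revised instructions and a few added questions at existing visits. The recorded rate of mild events will probably rise, and the study summary report should say that these effects were asked about directly.

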2.6 Pre-Treatment Procedures

If the subject is of childbearing potential (i.e. females not post-menopausal or not surgically sterile), they will be asked if they are pregnant, the date of their last menstrual cycle, and perform a urine pregnancy test. At each subsequent treatment, subjects will be asked the date of their last menstrual cycle for pregnancy verification purposes. A urine pregnancy test may also be conducted at the Investigator's discretion at any time during the study. If a urine pregnancy test is conducted, then a negative result must be obtained within 24 hours prior to the treatment.

Urine Pregnancy Test Procedure:

1. A urine sample is tested mid-stream or by cup sample with an indicator stick.
2. Negative results are indicated on the indicator stick.

- Photographs will be taken prior to the first treatment and may be taken prior to each subsequent treatment.

2.7 Treatment Procedures

- Procedures for the shock wave treatment:
 - The defined study area will be identified and will be cleansed thoroughly using a facial cleanser or mild soap and water. The treatment area may be marked with a marker.
 - The device may be used in accordance with the Protocol Manual and Instructions for Use.
 - Test spots may be performed prior to treatment in an area, such as on the hand, or in or close to the treatment area or so the subject can get used to the sensation.
 - Ultrasound gel will be applied to the area to be treated.
 - The applicator will be placed on the skin and slowly moved over the identified treatment area administering pulses of acoustic pressure shockwaves.
 - Parameters may be adjusted throughout the treatment to increase subject comfort.
 - Subjects will be asked to report the general level of treatment discomfort/pain on a scale of 0 (none) to 10 (maximum intolerable pain).
 - Parameters and tissue response will be continuously monitored and recorded during treatment.
- The additional treatments will follow the same procedure.
- Subjects and Clinicians may be asked to complete treatment questionnaires.
- Subjects may receive up to 5 treatments. Treatments will be performed every 3 – 14 days.

2.8 Post Treatment Procedures

- Adverse events will be documented after treatment.
- Photographs may be taken post treatment.
- Post treatment instructions will be reviewed with the subject.

2.9 Follow Up

- Subjects will return for follow up visits at 30 and 90 days post last treatment.
- Photographs will be taken and adverse events will be documented and each follow up visit.
- Clinician and subject questionnaires may be performed at each follow up visits.
- Any subject affected by COVID-19 that is not able to attend their follow up visits to complete the study will be asked to return to the site for a final follow up visit within 1 year of last treatment.
- Some subjects may have an incomplete response or no response by the end of the study. At the end of the study, treatments using an FDA approved/cleared treatment method may be discussed with the subject and obtained at the cost of the subject.

2.10 Biopsy Portion of the Study

- Subjects may enroll in the biopsy portion of this study. If the subject has signed the biopsy consent form and enrolled, the following will also be performed:
 - Biopsies may be taken from a treated area the day of treatment and/or may be taken 1, 3, 7 (+/- 1 day), 14 (+/- 2 days), 21 (+/- 2 days), and/or 30 days (+/- 3 days) post last treatment. A control will also be taken on the contralateral side of the treatment area.
 - Biopsy subjects may receive up to 6 biopsies.
 - A local anesthetic, such as lidocaine, may be injected to the area prior to biopsy.

- A 2 mm or 3mm punch biopsy (based on Physician assessment) will be taken from the treatment area.
- Sutures may be used to close the incision site.
- The subject may be asked to attend a 1 week (7-14 days) post each biopsy visit to remove the sutures and assess side effects.
- The following post biopsy treatment instructions will be reviewed:
 - Slight redness, initial tenderness to the wound site is normal; however, if you experience more redness, swelling, pain, pus, or drainage contact the study site immediately.
 - If the biopsy site begins to bleed, apply direct pressure for 10-20 minutes. If it continues to bleed, call the study site immediately.
 - Keep the wound dry today and remove bandage in 24 hours and leave off.
 - Avoid hot tubs, pools, and ocean until sutures are removed. Avoid soaking in water until 14 days after your biopsy.
 - When showering, wash carefully and do not scrub or traumatize the treated skin, or allow spray of shower to strike the skin directly. If the skin is treated harshly, this can increase the risk of scarring.
 - After showering, lightly pat dry the wound or let it air dry, then cover the biopsy site with an application of Vaseline (or petroleum jelly) at least 1-2 times daily. Keeping the wound moist reduces infection, minimizes scarring, and prevents crust formation over the wound.
 - Band-Aids (or any generic Adhesive Bandages) may be used for sleeping or in daily routines where the area may be rubbed/irritated. Whenever possible, keep Band-Aid (or generic Adhesive Bandage) off of the area and keep the area moist with Vaseline (or petroleum jelly) as previously described but do not allow drying out and forming a hard scab.
 - For any wound discomfort, you may take Tylenol as needed, or use cold compresses for up to 20 minutes hourly as needed. If using ice, it should be wrapped in a plastic and then a cloth to avoid burning your skin and wetting your bandage.
 - Avoid picking at the wound site, which increases risk of infection and scarring.
 - In order for the wound to heal properly and not leave bumpy scars, be careful not to overstretch the wound site area. As a wound heals, it will be weaker than the surrounding skin and can even "pop open" the sutures (stitches) if stretched too much. Sport or strenuous exercises that can pull at the wound site are best avoided for at least the next 3 days and up to one week.
 - Return for suture removal within 7 - 14 days as instructed per study protocol. If applied, Steri-strips must be kept dry as they are more likely to separate when wet. Steri-strips will usually fall off by themselves or you may be advised by the study doctor to remove them when the wound healed.
 - ONCE SUTURES ARE OUT: To minimize sore formation and to improve the final appearance of your skin, it is very important to keep the wound site area covered with the Vaseline for the next few days, until there is no more crust forming and the skin has completely healed.
 - Temporary discoloration at the wound site is normal and should gradually fade over the next few months. Please protect newly healed biopsied area with SPF and avoid sunburn.

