2.0 PROTOCOL

2.1 Protocol Methodology and Analysis

Methodology:

Subjects are to be enrolled in this clinical study if they are a healthy male or female 18 – 65 years of age. Up to 50 subjects will be enrolled at 2 study centers. Subjects will attend a screening/pretreatment visit which may be performed on the same day as the treatment visit. Subjects may receive up to 5 treatments with the study device. Subjects may also receive treatment

with a similar shockwave device. Subjects may be consented to have biopsies collected at a specific time after their final treatment, which will occur up to 30 days post treatment. Follow up visits may occur 30 and 90 days post last treatment visit. An unscheduled visit or phone call may be performed at any time during the study at the request of the subject or as deemed necessary by the site Investigator.

Analysis:

Upcoming generations are proving to have an interest in non-ablative aesthetic treatments and will drive demand for innovated products, procedures, and practice design.¹ Due to this shift in patient base, practices need to evolve to adapt to the newer generational ideologies. This device will be using the SoftWave device to collect additional data and imaging. Although this device is cleared for use by the U.S. Food and Drug Administration, there is a need to collect additional data, images, and tissue response to expand marketing claims.

Relevance:

There is an increasing demand for new methods and additional cleared indications for non-invasive treatments using shockwave therapy. Another device currently on the market cleared for use is, but are not limited to, the dermaPACE® System.

Testability:

The SoftWave device, had been previously cleared for the activation of connective tissue (FDA 510(k) K182682), the treatment of chronic, full thickness diabetic foot ulcers (FDA 510(k) K191961), and the treatment of superficial partial thickness second degree burns in adults (FDA 510(k) K200926). This study will utilize the collection of data and imaging to support additional marketing claims.

Compatibility:

Although shock wave technology is a well-known and widely use technique for non-invasive treatments, there is still a need to collect additional data and images, and expand marketing claims and device use.

Predictive power:

Assuming there is an acceptable side effect profile, it would be appropriate to expect results for other marketable indications.

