2.2 Protocol Study Design

This is a prospective, open label, multi-center clinical study to collect additional data and imaging for the SoftWave device.

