3.3 Risk Analysis

CONTEXT OF THE PROPOSED INVESTIGATION:

Shockwave is an effective approach to healing the human body using acoustic waves to stimulate the body's natural processes for self-repair. This technology is not new and although it has been in the marketplace for over 14 years in Europe, it just recently received FDA clearance in the US.

Shockwaves are created through the use of an electrode contained within a soft latex dome filled with water. When charged with electricity, the electrode creates a spark under the water. This spark creates a hot bubble of gas that expands into the surrounding water and produces the shockwave that travels out of the applicator and into the affected area being treated. These high energy acoustic waves penetrate deep into damaged tissue causing cellular walls to become permeable allowing exosomes to escape into the interstitial tissue mimicking cellular injury which triggers the migration of your body's own stem cells to the area for sustained long-term healing.

ASSESSMENT OF RISKS OF THE PROPOSED INVESTIGATION:

The risk identified with the overall clinical investigation is the integrity of the data collected. There are multiple clinical mitigation strategies for the risk identified. Proper training on the protocol will be performed. Monitoring of the study will be implemented to minimize subject and data risks.

ASSESSMENT OF BENEFITS OF THE PROPOSED INVESTIGATION:

The subject may or may not have improvement for the indication treated.

CONSIDERATION OF PATIENT PREFERENCE INFORMATION:

Many physicians support the use of shockwave devices for non-invasive treatments due to current patient satisfaction with their results with the currently available devices. However, there is still a level of interest in expanding indications and marketing claims for shockwave devices.

ASSESSMENT OF UNCERTAINTY:

There is uncertainty of efficacy results for expanding marketing claims while using the SoftWave device in this study.

CONCLUSION:

This study is determined to be a non-significant risk study and the risks posed to the subjects and integrity of data are acceptable.

Patient population to be enrolled in this clinical study:

Total anticipated population: 50 Subjects

Age Range: 18 – 65 years of age

Gender: Male or Female

Condition: Conditions that may be treated with the activation of connective tissue.

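### The biopsy comparison rests on one contralateral control, with no pre-treatment tissue and no stated way of choosing the treated side, so a treated-minus-control difference can reflect a side difference that was already there

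*Combined protocol and SAP*

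**What the plan says.** Section 1.2 lists tissue response, by staining and gene expression, as an additional, optional objective. Section 2.10 supplies the comparator: "A control will also be taken on the contralateral side of the treatment area". It does not say when the control is taken.

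For timing, section 2.10 lists biopsies from a treated area on the day of treatment and at 1, 3, 7, 14, 21 and 30 days after the last treatment. Section 2.1 agrees that sampling follows treatment: "Subjects may be consented to have biopsies collected at a specific time after their final treatment, which will occur up to 30 days post treatment". The schedule in section 2.13 marks biopsies at Visit 7 only, not at screening or pre-treatment. Section 2.10 also sets a limit: "Biopsy subjects may receive up to 6 biopsies".

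On the treated area, section 2.7 says: "The defined study area will be identified and will be cleansed thoroughly using a facial cleanser or mild soap and water". It names no person, side or rule. Section 2.2 describes the design: "This is a prospective, open label, multi-center clinical study to collect additional data and imaging for the SoftWave device". Section 2.15.3 defines analysis sets by patients who are randomized, but no section describes a randomisation of subjects or of sides.

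Section 2.3 asks for healthy subjects. Section 3.3, however, has the line "Condition: Conditions that may be treated with the activation of connective tissue", and the post-treatment instructions in section 2.5 tell subjects to "avoid extreme exercise or activities that may reinjure the damaged area through overuse".

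In section 2.15.1 the success criterion for biopsies is that they are collected. No treated-versus-control analysis is written.

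**The concern.** A contralateral control is sound when the two sides are exchangeable before treatment, or when the choice between them is made by chance. The plan secures neither. A baseline sample could have stood in for them, but none is planned.

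The difference between sides in one subject is the treatment effect plus whatever difference was there beforehand. If sites tend to treat the side with the complaint, the control is systematically the better side. A device with no effect on tissue could then appear to change it, or a real effect could be masked. The study is meant to support marketing claims (sections 1.1 and 2.1), and the revisions tracker in Appendix A shows that the control was added deliberately, so someone is likely to make the comparison. Once treatment has begun, baseline tissue cannot be recovered.

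**Working it through.** **Reading check.** Setting sections 2.1, 2.10 and 2.13 side by side, no listed biopsy time precedes treatment. Setting 2.2, 2.7, 2.10 and 2.15.3 side by side, no procedure for choosing the side appears.

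**The plan's own figure.** The only sample size is 50 subjects including departures (section 2.15.2). It has no effect size, SD or power behind it, so it cannot be reproduced. The number entering the biopsy portion is not given.

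**Model for an illustration.** For subject i let D_i = T + S_i + e_i, where D_i is treated minus control, T is the device effect, S_i is the pre-existing difference between the chosen and the opposite side, and e_i is noise.

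- If S_i has mean zero because the choice is unrelated to the tissue, D_i has mean T. The variation in S_i adds noise only.
- If S_i equals a constant S, D_i has mean T + S. The data cannot separate the two.

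**Assumed inputs, none of them in the documents.** T = 0; one paired difference per subject; paired t-test, two-sided 0.05; d = S / SD(e) = 0.2, 0.3, 0.5 or 0.8; n = 10, 20 or 30. The plan states the 0.05 level only for demographic and medical history comparisons (section 2.15.4).

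**Formula.** With c the 0.975 quantile of t on n − 1 degrees of freedom, and F the noncentral t distribution function on n − 1 degrees of freedom with noncentrality d√n:

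P(reject) = 1 − F(c) + F(−c).

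Example: n = 10, d = 0.5. c = 2.262, noncentrality = 0.5 × √10 = 1.581, P(reject) = 0.293.

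| d | n = 10 | n = 20 | n = 30 |
|---|---|---|---|
| 0 | 5.0% | 5.0% | 5.0% |
| 0.2 | 8.8% | 13.6% | 18.5% |
| 0.3 | 13.6% | 24.7% | 35.5% |
| 0.5 | 29.3% | 56.5% | 75.4% |
| 0.8 | 61.6% | 92.4% | 98.8% |

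**With the side randomised.** S_i becomes +S or −S with equal probability, so its mean is zero. In 100,000 simulated trials per cell, for the same non-zero d and n, the rejection rate was about 5% throughout (4.9% to 5.1%).

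Randomising turns the bias into variance. The SD of D_i rises by a factor √(1 + d²): √1.09 = 1.04 at d = 0.3, √1.25 = 1.12 at d = 0.5, √1.64 = 1.28 at d = 0.8.

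**Room for a baseline biopsy instead.** Section 2.10 lists seven times (0, 1, 3, 7, 14, 21, 30 days). With one control that makes 7 + 1 = 8 possible samples against a limit of 6. A baseline pair would add to a list that already exceeds the limit if every time were used. Side randomisation adds no samples.

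**The case against.** The strongest reply is that a biased mean needs a side difference running the same way across subjects, and the documents do not show one. Section 2.3 enrols healthy people. The damaged-area wording sits in post-treatment instructions that may be generic, and the condition line in section 3.3 names no disease and no side. In healthy volunteers with no systematic choice, side differences are mostly noise. This stands: a consistent difference is plausible, not demonstrated.

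A reader might infer that the operator picks the treated side. The documents do not say so; section 2.7 is passive and names nobody. What can be said is that no method is specified.

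A reader might also infer that the plan will read side differences as tissue response. It does not go that far. No treated-versus-control test is planned, and biopsy success means collection. The error rates above therefore belong to an analysis supplied here for illustration.

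Serial samples from the treated side offer partial protection, since a stable side difference would not produce a change over time. But serial sampling is optional, section 2.1 speaks of one specific time, and the schedule counts days from the last treatment, so even its day-0 sample is treated tissue.

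**Conclusion.** The gap is real: one contralateral control, no pre-treatment tissue and no rule for the side. As designed, a treated-minus-control difference in staining or gene expression cannot be separated from a side difference already present. Whether that biases the mean depends on whether the choice of side is related to the tissue, which the documents leave open. If it is not, the cost is noise only.

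The size is conditional. A false-positive rate of 14% to 62% at n = 10, rising to 36% to 99% at n = 30, for consistent differences of 0.3 to 0.8 SD, rests on an assumed test, assumed sample sizes and assumed differences. At 0.2 SD and n = 10 it is about 9%, and at zero it is the nominal 5%.

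The objective is optional and additional, and the primary pain objective is untouched. The change is worth making because it is cheap and cannot be made afterwards, but it ranks below points on the primary objective.

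**What to change.** In section 2.10, for biopsy subjects whose treatment area could be on either side, assign the treated side (left or right) from a computer-generated random list. Open each entry after the biopsy consent is signed and eligibility is confirmed, and before the area is identified and marked for the first treatment. Issue of the subject number is not a sufficient trigger, because the biopsy consent is a separate form and may be signed later. Take the control from the corresponding opposite site, state when it is taken, and compare treated with control within subject.

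Subjects who cannot be randomised, because the condition is one-sided or because biopsy consent came after treatment began, should have their tissue results reported separately and descriptively. If the sponsor prefers not to randomise, the minimum is to state how the side is chosen and to label all treated-versus-control tissue results descriptive.

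Cost: a short passage in section 2.10 and a list. No extra biopsies, visits or staff are needed. Free choice of side is lost for biopsy subjects, fewer subjects may count in the tissue comparison, and the paired differences are somewhat noisier where a side difference exists.
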